9.9.8 Controlling Type I Error

To control the two-sided type I error over all the efficacy endpoints that are intended to support potential claims, the primary and key efficacy endpoints will be tested in the following sequential order at significance level 0.01; as soon as an efficacy endpoint test is non-significant at $\alpha=0.01$, the testing procedure stops for all subsequent endpoints:

- Time to diagnosis of MCI due to AD for pioglitazone-treated, non-Hispanic/Latino Caucasian subjects versus placebo-treated non-Hispanic/Latino, Caucasian subjects in the high-risk stratum.
- Change from baseline to Year 4 for cognitive decline on composite score on the cognitive battery for pioglitazone-treated, non-Hispanic/Latino Caucasian subjects versus placebo-treated non-Hispanic/Latino, Caucasian subjects in the high-risk stratum.
- Changes from baseline to Year 4 in instrumental activities of daily living (Alzheimer's Disease Cooperative Study Activities of Daily Living - Prevention Instrument [ADCS-ADL-PI]) for pioglitazone-treated, non-Hispanic/Latino Caucasian subjects versus placebo-treated non-Hispanic/Latino, Caucasian subjects in the high-risk stratum.

9.9.9 Analysis of Additional Variables

Except where otherwise noted, summaries and analyses for additional variables will be done using the FAS subjects in primary efficacy analysis population (high-risk, non-Hispanic/Latino subjects). Except for analyses involving the primary and key secondary endpoints, all other analyses (ie, analyses of additional variables) will be done using a significance level of 0.05.

The incidence of MCI due to AD will also be compared using a chi-squared test, and the difference in incidence will be reported along with 95% confidence intervals.

Relatively few cases of AD are anticipated. The incidence AD will be compared using a chi-squared test, and the difference in incidence will be reported along with 95% confidence intervals. Cases of AD will be described in the listings.

For continuous endpoints which are collected at multiple scheduled visits, change from baseline will be analyzed by study visit using MMRM analysis of covariance.

Although change-from-baseline endpoints will be assessed at all visits, the primary time frame for purposes of efficacy analysis is the change from baseline to Month 48 (Year 4).

The change from baseline variables for the BVMT-R test (BVMT_T1, BVMT_T2, BVMT_T3, BVMT_TOT, BVMT_DEL, and BVMT_COPY) will each be analyzed as a continuous variable by study visit using an MMRM model similar to the ones described above for the key secondary variables.

The change from baseline variables for the Trail Making Tests (Trails A time and Trails B time) and WAIS-III digit span tests (forward span, backward span, and total) will each be analyzed as a continuous variable by study visit using an MMRM model similar to the ones described above for the key secondary variables.

For the variables BVMT_HIT, BVMT_FP, and BVMTDISC, TRAILS AE, and TRAILS BE, counts and percentages of each possible value will be tabulated and summary statistics (n, mean, SD, median, minimum, and maximum) will be given by treatment group (including low-risk placebo) for the actual values and change-from-baseline values for each visit and EoS/EW.

The change from baseline variables for the MINT, semantic and lexical fluency test variables (SEMFLU, LEXFLU, LEX_F, LEX_A, and LEX_S), and Clock Drawing Test will each be analyzed as a continuous variable by study visit using an MMRM model similar to the ones described above for the key secondary variables.

The change from baseline variables for the CVLT-II test (CVLT_T1, CVLT_T2, CVLT_T3, CVLT_T4, CVLT_T5, CVLT_TOT, CVLT_TB, CVLTSDEL, CVLTLDEL, CVLTINTR, CVLT_REP, CVLTHITS, and CVLT_FP) will each be analyzed as a continuous variable by study visit using an MMRM model similar to the ones described above for the key secondary variables.

The change from baseline variables for the cognitive battery domain scores (memory, executive function, language, and attention) will each be analyzed as a continuous variable by study visit using an MMRM model similar to the ones described above for the key secondary variables.

The change from baseline variables for GDS Total score, ADCS MCFSI total score, IQCODE Overall mean score, and ADCS ADL-PI Physical Function total score will each be analyzed as a continuous variable by study visit using an MMRM model similar to the ones described above for the key secondary variables.

The ADCS-CGIC-MCI total, cognition, behavior, and functional ability scores will each be analyzed as continuous variables by study visit using a MMRM models similar to the ones described above for the key secondary variables (using the appropriate corresponding ADCS-CGIC-MCI baseline score). In addition, each of these 4 ADCS-CGIC-MCI variables will be analyzed at the last visit using the Cochran-Mantel-Haenszel test and stratifying by center.

The MMSE total score is scheduled to be collected at 6-month visits and EoS/EW. Summary statistics will be used to present MMSE total score and change from baseline in MMSE total score at EoS/EW.

The CDR and NPI-Q are scheduled to be collected at baseline and EoS/EW. The CDR Global Score and domain scores will be presented using shift tables from baseline to EoS/EW. Summary statistics will be used to present CDR-SB and change from baseline in CDR-SB at EoS/EW. In addition, each of the 6 CDR domain scores at Baseline and at each time point when MCI due to AD was diagnosed will be included in the listings.

For each of the NPI-Q variables Total Severity Score and Caregiver Distress Score, the change from baseline in NPI-Q from baseline to EoS/EW will be analyzed using an ANCOVA model analogous to the model for the key secondary endpoints. The following SAS code will be used for the ANCOVA analysis:

- Proc mixed data=all;
- class treat center gender;

- model Change = Baseline treat center gender education age;
- lsmeans treat / cl pdiff;

In the above model, baseline is the baseline value and Change is the change from baseline value.

Volumetric MRI (vMRI) variables were collected in a substudy of approximately 300 subjects. These volumetric MRI atrophy and enlargement endpoints are calculated with sophisticated algorithms that derive the change in the brain by registering each of the follow-up time points against the baseline and calculating algorithmically the change (ie, this is not determined by calculating the volume at baseline and then independently calculating the volume at a given post-baseline visit and then subtracting). The vMRI variables left hippocampal atrophy, right hippocampal atrophy, whole brain atrophy, and ventricular enlargement will each be analyzed as continuous variables by study visit using ANCOVA models similar to the ones described above for the NPI-Q variables. The appropriate baseline variable (ie, left hippocampal volume, right hippocampal volume, whole brain volume, or ventricular volume), as well as intracranial volume, will be used as covariates in each of these models.

For each efficacy variable for which MMRM analysis of covariance analyses will be done, summary statistics (n, mean, SD, median, minimum, and maximum) by treatment group (including low-risk placebo) will be given for the actual values and change-from-baseline values for each visit and EoS/EW.

For the single-item variables MMSE_i, GDS_i, ADCS_i, EQ5D_i, SF36_i, IQ_i, ADLQ_i, and NPIQ_i, the counts and percentages of each possible value will be tabulated by treatment group (including low-risk placebo) for each visit and EoS/EW. For single-item variables which have a meaningful numerical score, summary statistics (n, mean, SD, median, minimum, and maximum) by treatment group (including low-risk placebo) will be given for the actual values and change-from-baseline values for each visit and EoS/EW.

MRIs will be done as part of the comprehensive medical follow-up evaluation to rule out other causes of dementia and confirm the clinical diagnosis of MCI due to AD (see Section 6.2.4 of the protocol). For subjects who have contraindications for the MRI procedure (such as unremovable ferromagnetic dental work, cardiac pacemakers, etc) a CT scan can be done instead. The possible categories for the interpretation results are: Within Normal Limits; Abnormal, Not Clinically Significant; and Abnormal, Clinically Significant. The last available MRI/CT scan interpretation results for each subject will be summarized by treatment group, and all MRI/CT scan interpretation results will be presented in the listings.

Except for time-to-event analyses and the summary of MRI interpretation results, unscheduled visit values will be excluded from the summaries and analyses but will be included in the end-of-text CSR listings.

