9.1.15 Assessments

9.1.15.1 Cognitive Test at Screening

At the Screening Visit, subjects will be tested to determine if their cognitive status qualifies them for entry to the study. The screening instrument will be the MMSE [47]. The MMSE is a measurement of global cognitive function, includes 11 items that assess orientation to time and place, language, verbal registration, memory, and praxis. Scores on this instrument range from zero to 30, with lower scores indicating greater cognitive impairment. At the Screening Visit, MMSE scores should always be adjusted for education and age (Appendix G). Scores ≤ 24 after age and education adjustment are considered impaired. The MMSE will also be collected at the Baseline Visit, every 6 months after randomization (ie, each Study Visit), and at the EoS/EW Visit.

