Appendix A Schedule of Study Procedures (continued)

	Screening Visit 1	Base-line Visit 2	Random-ization Visit 3	Double-Blind Treatment Repeated yearly				Unscheduled - CMFV (q) (v)	EoS / EW Visit (b) (j)	Follow-up Visit (c)
				3 (a)	6	9 (a)	12			
Study Month:	-4	-1	0 (Day 0)	3 (a)	6	9 (a)	12			EoS/EW+0.5
Visit Window (t):	Max Day -125	Max Day -35		±2 weeks	±2 weeks	±2 weeks	±2 weeks	Within approx. 30 days of trigger		
Efficacy (continued)										
GDS		X			X		X		X(u)	
ADCS-MCFSI		X			X		X		X(u)	
EQ-5D		X						X	X(u)	
SF-36		X						X	X(u)	
IQCODE		X			X		X		X(u)	
ADCS ADL-PI		X			X		X		X(u)	
NPI-Q		X						X	X(u)	
ADCS-RUI		X			X		X	X	X(u)	
CDR		X						X	X(u)	
ADCS-CGIC- MCI		X			X		X	X (u)	X(u)	

Footnotes are on the following page.

Excl=exclusion, Incl=inclusion.

- (a) Telephone contact (should be every 3 months between the semi-annual clinic visits for the life of the study).
- (b) EoS/EW Visit is an ad hoc visit that, for study completion, would take place as soon as possible after a regularly scheduled Study Visit, either after the CIAC has confirmed that the subject has reached the MCI due to AD primary endpoint event (or any other irreversible cognitive impairment or dementia) or after a subject has withdrawn prematurely from the study. In cases where the endpoint has been reached, the efficacy assessments will not need to be captured at this Visit.
- (c) Subjects will have a safety follow-up call 2 weeks after completion or withdrawal. Subjects who withdraw their consent should still be contacted for a safety follow-up call, but the contact should only be recorded in the medical records (and not in the [e]CRF), according to data protection regulations.
- (d) footnote deleted
- (e) Please refer to Section 10.2.1.3.
- (f) As part of the comprehensive medical follow-up evaluation to rule out other causes of dementia and confirm the clinical diagnosis of MCI due to AD (See section 6.2.4). An MRI scan is not required to be performed if a study related MRI scan was collected within 6 months of the CMFV. For subjects who have contraindications for the MRI procedure (such as unremovable ferromagnetic dental work, cardiac pacemakers, etc) a CT scan can be done instead.
- (g) DNA sample expected to be collected at this visit, but if necessary, may be collected at any visit after randomization.
- (h) Sites should make every attempt complete the cognitive test battery in the order of outlined in Section 9.1.17.

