9.9 Efficacy Analyses

Except as otherwise noted, the analyses and summaries will be based on the FAS.

All primary and key secondary efficacy analyses and summaries will be presented separately for the following groups of subjects:

- Non-Hispanic/Latino Caucasian subjects.
- Hispanic/Latino and/or non-Caucasian subjects.
- All subjects.

All primary, secondary, additional, and other outcomes variables listed below will be presented by treatment group using descriptive statistics by visit (including change-from-baseline for continuous variables) and presented in efficacy listings.

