9.9.1 Overview of Primary, Secondary, and Additional Variables

The primary, secondary and additional variables for this study are presented in [Table 9.b](#). While most of the variables in the table are technically discrete, the variable type column indicates how the variables will be considered for purposes of analysis.

Table 9.b Primary, Secondary and Additional Variables

Parameter	Description	Range	Variable Type
MCI_TIME	Time to event of MCI due to AD	N/A	Time-to-event
MMSE	Total of all items correct	0-32	Continuous
MMSE _i	MMSE single item i	0-5	Categorical
BVMT_T1	# of elements recalled, Trial 1 (0-12 possible)	0-12	Continuous
BVMT_T2	# of elements recalled, Trial 2 (0-12 possible)	0-12	Continuous
BVMT_T3	# of elements recalled, Trial 3 (0-12 possible)	0-12	Continuous
BVMT_TOT	Total # of elements recalled, Trials 1-3	0-36	Continuous
BVMT_DEL	Total # of elements recalled after a delay (25-minute delay)	0-12	Continuous
BVMT_HIT	Total # of target elements correctly recognized	0-6	Continuous
BVMT_FP	Total # of foils incorrectly endorsed	0-6	Continuous
BVMTDISC	Total target elements correctly recognized relative to Total false positives	-6 to 6	Continuous
BVMTCOPY	Total # of elements copied correctly	0-12	Continuous
DIGIT_F	Total items correct, Digit Span Forward	0-16	Continuous
DIGIT_B	Total items correct, Digit Span Backward	0-14	Continuous
DIGITOT	Total Forward + Back	0-30	Continuous
TRAILSAS	# of seconds to complete all items, Trails A	0-300	Continuous
TRILSAE	Errors (number of errors committed during the test)	0-5	Continuous
TRAILSBS	# of seconds to complete all items, Trails B	0-300	Continuous
TRILSBE	Errors (number of errors committed during the test)	0-15	Continuous
MINT	Total correct, MiNT	0-32	Continuous
SEMFLU	Number of exemplars generated in 1 minute (up to max=100)	0-100	Continuous
LEXFLU	Number of exemplars generated total for F, A, and S (up to max 267)	0-267	Continuous
LEX_F	Number of exemplars generated in 1 minute (up to max=89)	0-89	Continuous
LEX_A	Number of exemplars generated in 1 minute (up to max=89)	0-89	Continuous
LEX_S	Number of exemplars generated in 1 minute (up to max=89)	0-89	Continuous
CLOCK	Number of elements correct (eg, clock face, hands, number placement), Clock Drawing Test	0-10	Continuous
CVLT_T1	# of words (out of 16), recalled 1st trial	0-16	Continuous
CVLT_T2	# of words (out of 16), recalled 2nd trial	0-16	Continuous
CVLT_T3	# of words (out of 16), recalled 3rd trial	0-16	Continuous

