- Second, if the conditional power value is $>30\%$ (see Section 9.16.1), then the DSMB will make a recommendation to the Executive Committee that the study is non-futile with respect to efficacy. In this case, the study will continue unchanged, and the Executive Committee will remain blinded.
- If the conditional power value is $\leq 30\%$, then the DSMB will receive the additional planned unblinded analyses (described below) from the [CCI] Unblinded Statistician.

- MMRM analyses by visit (including all visits for which at least 50% of the subjects have non-missing values) based on the composite score key secondary endpoint related to changes from baseline in cognition.
- MMRM analyses by visit (including all visits for which at least 50% of the subjects have non-missing values) based the following components of the composite score key secondary endpoint.
 - CVLT-II Long-Delay Free Recall
 - CVLT-II Short-Delay Free Recall
 - BVMT-R Delayed Recall
- MMRM analyses by visit (including all visits for which at least 50% of the subjects have non-missing values) for MMSE total score.
- Summary statistics by visit for all of the above-described CLVT-II, BVMT-R, CDR-SB, and MMSE total score continuous endpoints for all visits. For CDR-SB, visit will be derived using visit window defined in Section 9.1.3.
- CCI 
- For the longitudinal model, a linear trajectory model (SPM1L) will be used to model the change in the continuous efficacy endpoint over time. This model is chosen because the futility analysis is likely at an early stage of the disease development and treatment effect. Treatment and treatment*time will be included to evaluate the effect of treatment on the progression of the continuous efficacy endpoint. Values of the continuous endpoint will be used as the response in the model. Baseline value will be coded as the response at time 0. Other covariates (age, years of education, gender, and pooled center) that are included in the MMRM model for the change from baseline in the composite score will also be included in the longitudinal model.

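### SAP 9.9.9 is inconsistent on MMSE total score: its general rule implies a by-visit MMRM, but the MMSE sentence names only EoS/EW summary statistics

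*SAP*

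**What the plan says.** **Collection.** Protocol 9.1.15.1: "The MMSE will also be collected at the Baseline Visit, every 6 months after randomization (ie, each Study Visit), and at the EoS/EW Visit". SAP 9.9.9 agrees: "The MMSE total score is scheduled to be collected at 6-month visits and EoS/EW". Table 9.b in SAP 9.9.1 describes the MMSE row as "Total of all items correct" and types it as continuous.

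**General rule, SAP 9.9.9.** "For continuous endpoints which are collected at multiple scheduled visits, change from baseline will be analyzed by study visit using MMRM analysis of covariance". The same section makes Month 48 the primary time frame for change-from-baseline endpoints and sets 0.05 as the level for additional variables.

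**MMSE sentence, SAP 9.9.9.** "Summary statistics will be used to present MMSE total score and change from baseline in MMSE total score at EoS/EW". No model and no 6-month visit is named.

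**Descriptive rule, SAP 9.9.** All primary, secondary, additional and other-outcome "variables listed below will be presented by treatment group using descriptive statistics by visit (including change-from-baseline for continuous variables").

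**Futility look, SAP 9.16.** If conditional power is 30% or less, the DSMB receives further analyses, among them "MMRM analyses by visit (including all visits for which at least 50% of the subjects have non-missing values) for MMSE total score".

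**EoS/EW visit, Protocol Appendix A.** MMSE is listed under Efficacy and marked at EoS/EW. Footnote (b) to that column adds: "In cases where the endpoint has been reached, the efficacy assessments will not need to be captured at this Visit".

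**The concern.** The MMSE sentence acknowledges the 6-monthly schedule and then plans a summary at the exit visit alone. A programmer who follows it would produce no treatment estimate, confidence interval or p-value for MMSE. A programmer who follows the general rule would produce all three. If the choice is settled only after unblinding, whether MMSE receives a nominal p-value becomes a post hoc decision.

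The one visit that the sentence names is also the least suitable. Confirmed converters may have no MMSE there, and they are the subjects most likely to have declined. If pioglitazone works as planned, more of them are on placebo, so the missing values would depend on treatment. Exit times also differ between subjects, so an EoS/EW summary mixes different lengths of follow-up.

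**Working it through.** **Step 1. Does MMSE meet the general rule?** The rule has two conditions.

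| Condition | MMSE total score | Source |
|---|---|---|
| Continuous | Yes | SAP Table 9.b |
| Collected at several scheduled visits | Yes, every 6 months | Protocol 9.1.15.1; SAP 9.9.9 |

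Both are met, so the general rule read alone gives MMSE an MMRM.

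**Step 2. Does a specific sentence override the rule?** Elsewhere in SAP 9.9.9 it does.

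- The BVMT-R recognition hits, false positives and discrimination score, and the Trails A and B error counts, are also typed as continuous and belong to tests given every 6 months. Their own sentence assigns them counts, percentages and summary statistics only.
- MMRM is assigned by name to the BVMT-R recall and copy scores, Trails times, digit span, MINT, fluency, clock drawing, CVLT-II, domain scores, GDS, MCFSI, IQCODE, ADL-PI Physical Function and CGIC. MMSE is not in those lists.
- The section says that each variable with an MMRM will have summary statistics at every visit and EoS/EW. The MMSE sentence names EoS/EW alone, which fits a variable that is not meant to be modelled.

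The descriptive-only reading is therefore plausible, although the text does not exempt MMSE in so many words.

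**Step 3. Does another section settle it?**

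- SAP 9.9 supplies by-visit descriptive tables by arm, but no model.
- SAP 9.9.9 tabulates the single MMSE items by arm at each visit, again without a model.
- SAP 9.16 supplies an MMRM, but only at the futility look and only if conditional power is 30% or less.
- SAP 9.17, on changes from the protocol analysis, does not mention MMSE.

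**Step 4. How many subjects can the EoS/EW summary omit?** The plan gives no figure for this, so it is built from the design inputs in SAP 8.0: 15% and 9% events over 5 years, 12% annual drop-out, two-sided alpha 0.01, 90% power, 202 events.

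Reproducing the event target first:

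- Hazard ratio = ln(0.91)/ln(0.85) = 0.580.
- Schoenfeld events = 4 × (2.576 + 1.282)² / (ln 0.580)² ≈ 201, against the stated 202.

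Share of the high-risk primary population:

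- 202/2,346 = 8.6% (minimum sample size).
- 202/2,940 = 6.9% (expected enrolment).

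Expected split by arm, with exponential event and drop-out times:

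- Annual hazards: placebo −ln(0.85)/5 = 0.0325; pioglitazone −ln(0.91)/5 = 0.0189; drop-out −ln(0.88) = 0.1278.
- Probability of conversion before drop-out by time T = h/(h + d) × [1 − exp(−(h + d)T)], where h is the event hazard and d the drop-out hazard.
- At T = 5: placebo 0.1118, pioglitazone 0.0668.
- Scaled to 202 events: placebo 202 × 0.1118/(0.1118 + 0.0668) ≈ 126; pioglitazone ≈ 76.
- With T = 4 or 5.5 the split is 126.7 to 75.3 or 126.3 to 75.7, so the assumed follow-up hardly matters.

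The probabilities are used only for the split. The total is held at 202 because the trial is event-driven.

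Per arm, 126 and 76 are 10.7% and 6.5% of 1,173, or 8.6% and 5.2% of 1,470.

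**The case against.** The strongest reply is that the general MMRM rule already covers MMSE. The MMSE sentence does not contain the word only and does not exempt the score, so it can be read as adding an EoS/EW summary to the by-visit model. The fix would then restate what the SAP already says. That reading is available and cannot be ruled out. What stands against it is the pattern in Step 2: specific sentences do displace the rule in this section, and nothing tells the reader that this one does not.

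The reply also limits what can be claimed. Four stronger inferences are tempting, and the documents do not support them.

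- *The final report will contain no between-arm view of MMSE.* SAP 9.9 requires by-visit descriptive statistics by arm, and the general rule may supply a model as well.
- *Overall cognition goes unmodelled because MMSE is the only global measure followed throughout.* The battery composite is a key secondary endpoint with an MMRM, and the four domain scores and ADCS-CGIC-MCI are modelled by visit too.
- *A routine MMSE model at the futility look is dropped at the end.* That model runs only if conditional power is 30% or less.
- *The EoS/EW summary hides a known difference in MMSE points.* The documents give no MMSE decline for converters or others, so no such figure can be derived. Footnote (b) permits omission of the assessments; it does not say that they will all be missing.

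**Conclusion.** The concern holds as an inconsistency within SAP 9.9.9. The general rule and the MMSE sentence point to different final analyses, so no between-arm MMSE model is clearly specified. The EoS/EW summary that is named can lose up to 202 converters, about 7% to 9% of the high-risk primary population, with roughly 126 expected on placebo and 76 on pioglitazone.

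The 202 is an upper bound: it is reached only if every converter skips the EoS/EW assessment. The split rests on the design event rates, 12% annual drop-out and exponential times.

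The consequence is limited. MMSE is outside the testing sequence in SAP 9.9.8, so type I error control and the primary and key secondary conclusions are unaffected, and any MMSE p-value would be nominal. This is a clarification worth making because it costs almost nothing and uses data already collected.

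**What to change.** Amend SAP 9.9.9 before unblinding, along these lines: *Change from baseline in MMSE total score will be analysed by study visit with the MMRM used for the key secondary variables, using the 6-month visits, with the Month 48 treatment contrast reported at a nominal 0.05 level. MMSE at EoS/EW will be summarised descriptively, with the number of confirmed converters without an EoS/EW value shown by arm.*

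Converters' MMSE values at the 6-month visits before they leave the study then contribute to the treatment comparison. The model does not recover values after conversion; as for the key secondary endpoints, it treats them as missing at random.

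If the sponsor instead intends MMSE to be exempt from the general rule, the section should say so and give the reason.

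The cost is one amended passage, one more run of an existing model and one count by arm. No new data, visits or subjects are needed.
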